### **7.3 Analysis**

The sequences will be analysed using the latest bioinformatics tools (like Dada2) and analysis will be done with the R software. The alpha diversity will be evaluated using Shannon's Diversity index and Simpson's diversity index; the beta diversity will be assessed by using Bray-Curtis dissimilarity, Jaccard distance and permutational multivariate analysis of variance. Differences will be considered statistically significant with a P-value  $\leq 0.05$ . (19, 20)

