between application and sampling. Indeed, the described effect could also be due to the diluting effect of the drop itself. In any case, when using a topical anesthetic drop, the firmness of the sampling can be considered influenced. Possibly there is a vertical stratification with the presence of transient species in the more superficial layers and a more resident commensal microbiota in the deeper layers (7).

To compare the effect of anesthetic drops, we decided to sample volunteers undergoing general anesthesia for any type of surgery. The right and left eye of one person will be randomized for a drop of artificial tears (Thealoz duo®, Théa Pharma, Clermont – Ferrand, Cedex 2, France) or a drop of topical anesthesia (Minims® Oxybuprocaine Hydrochloride 0.4%, Bausch and Lomb, Aubenas, Frankrijk). One drop of Thealoz duo® has the same weight as one drop of Minims® Oxybuprocaine Hydrochloride 0.4%, (both 0,02 g), this makes the diluting effect comparable. The executer will be blinded. The rationale for general anesthesia is that the sampling pressure/depth will be similar with or without topical anesthesia since the executer won't be influenced by the patients reaction. By comparing both eyes of one person, the immunological and genetic background will be the same. Moreover, Shalabi et al. showed a high level of concordance in microbiome composition in the same-person eyes (13). The effect of environmental factors, such as the effect of repeatedly sleeping on one side, will be minimalized by randomization. To have the possibility to take the most obvious confounding factors in account, subjects will be asked to fill in a small questionnaire (*see addendum A*).

In gut and oral microbiome research, it is currently acknowledged that the used **DNA extraction method** plays a crucial role in the recovery of microbial taxa (14-16). However, researchers focusing on less studied human microbial niches, like the ocular surface, seem not yet to be aware of the impact thereof. The ideal extraction protocol should reflect the microbial richness and diversity present on the eye as adequate as possible since the DNA extraction method affects the observed species diversity downstream. We aim at comprehensible integration of the results from the scarce microbiota studies published in this field, by

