**Colour code**  
DNeasy PowerSoil® Kit  
DNeasy Blood & Tissue® Kit  
Nucleospin® tissue  
QIAamp DNA microbiome® kit (with human depletion)  
RNeasy PowerMicrobiome® Kit  
FastDNA™ Spin Kit for Soil  
QIAamp DNA microbiome® kit (without human depletion)

*Figure 1*

Although the immunological and genetic background in one person are the same and [Shalabi et al.](#) showed a high level of concordance in microbiome composition in the same-person eyes (13), the environmental factors may differ between eyes. First of all, patients are known unilateral eye rubbers, with sometimes clinical consequences such as keratoconus (17). Secondly, repeatedly sleeping on one side can have an effect on the ocular surface microbiome as well due to rubbing of the eyelid against the pillow and nocturnal eyelid eversion (18). To further clarify the effect of environmental factors on both eyes within one individual, the 7 volunteers mentioned before will be asked to fill in a questionnaire (*cfr. addendum A*).

The **ambition** of this study is to make our research done in this area more robust since it will determine our method used in each future project.

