## 2. Trial objectives and design

We aim at clarifying 1) if the reported effects of the use of anaesthetic drops (9) are due to dilution of samples or not, 2) how different DNA extraction protocols distort our view on ocular

Study protocol EPSO v 7.0 dd 01.02.2021:

Optimization of sampling for molecular microbial research on ocular surface samples and building a framework for comparing current sequencing results using different extraction protocols.

surface microbiota composition and 3) the degree of similarity between left and right eye in the same person.

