## 7. Statistics

### 7.1 Sample size

Since this is an **exploratory study**, we are not able to perform proper sample sizing.

For the first part, we aim at sampling 30 patients (60 samples) taking into account a maximal loss of 10 samples due to processing issues. Taking this loss into account, we will be able to

Study protocol EPSO v 7.0 dd 01.02.2021:

Optimization of sampling for molecular microbial research on ocular surface samples and building a framework for comparing current sequencing results using different extraction protocols.

[figure not shown]
process 50 samples to elucidate if the use of anesthetic drops has an effect on the sequencing results.

For the second part, we wish to sample 7 volunteers so we can compare 7 extraction protocols on different subjects on non-consecutive days. Each protocol will be tested on a sample from a different individual on a different day (*figure 1*) to minimize possible confounding factors. In gut and oral microbiome research, samples are homogenized to make comparing of different extraction protocols possible. In ocular surface samples, the retrieved sample is too small for homogenization.

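### Part 1 pairs the two eyes of each patient, but Section 7.3 does not say that the analysis will use the pairing

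*Combined protocol and SAP*

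**What the plan says.** Part 1 is a within-patient design. Section 1 states: "The right and left eye of one person will be randomized for a drop of artificial tears" or a drop of topical anaesthetic. Section 2.1 (Part 1) repeats one product per eye, and the list in Section 7.2 has one entry per patient that sets which eye receives the anaesthetic. Section 1 gives the reason: "By comparing both eyes of one person, the immunological and genetic background will be the same". It also cites a study reporting close agreement between the two eyes of a person.

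Section 7.3 covers all three parts of the study in one short paragraph. For composition, "the beta diversity will be assessed by using Bray-Curtis dissimilarity, Jaccard distance and permutational multivariate analysis of variance". For alpha diversity it names the Shannon and Simpson indices but no test. The significance threshold is P ≤ 0.05. There is no patient term, no paired comparison and no permutation scheme.

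Section 7.1 states: "we aim at sampling 30 patients (60 samples) taking into account a maximal loss of 10 samples due to processing issues". What remains is expressed in swabs only: the study will "process 50 samples to elucidate if the use of anesthetic drops has an effect". It does not mention pairs or say how a patient left with one usable swab is handled.

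The first aim (Section 2) is to find out "if the reported effects of the use of anaesthetic drops (9) are due to dilution of samples or not".

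**The concern.** The pairing is the main strength of Part 1, because differences between patients cancel when each patient is compared with himself or herself. That benefit is realised only if the analysis uses the pair. PERMANOVA with freely permuted labels, or a two-sample test on the indices, treats fellow eyes as unrelated swabs and puts between-patient variation back into the error term.

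With positively correlated eyes, the error is then overstated: the true type I error falls below 5%, and power is lost relative to the within-patient analysis. A null result is a substantive answer to the first aim, so a reader would need to know whether it reflects no effect or an analysis that discarded information.

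**Working it through.** **1. The plan's own figure.** 30 patients × 2 eyes = 60 swabs; 60 − 10 = 50. This reproduces Section 7.1.

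**2. Complete pairs behind 50 swabs.** If b patients lose both swabs, then 10 − 2b patients lose one. Complete pairs = 30 − b − (10 − 2b) = 20 + b, with b from 0 to 5. The range is 20 to 25 pairs. If the ten losses fall at random (assumed), the mean is 30 × (50/60) × (49/59) = 20.76, or about 21 pairs with 8 single swabs. With no loss there are 30 pairs.

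**3. What a paired test can detect.** Two-sided 5% (sidedness assumed), 80% power, noncentral t. The detectable difference is λ/√n in SDs of the within-patient differences, where λ is the noncentrality needed:
- 20 pairs: 2.954/√20 = 0.66
- 25 pairs: 2.920/√25 = 0.58
- 30 pairs: 2.899/√30 = 0.53

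**4. Direction of the error if the pair is ignored.** Let one swab have variance σ² and fellow eyes have correlation ρ. With n complete pairs, the difference in means has variance 2σ²(1 − ρ)/n, but an unpaired test uses 2σ²/n. Its true type I error is about 2[1 − Φ(1.96/√(1 − ρ))]:
- ρ = 0.3: 1.96/0.837 = 2.34, giving 1.9%
- ρ = 0.5: 1.96/0.707 = 2.77, giving 0.56%

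With 21 pairs plus 4 single swabs per arm, the factor 1 − ρ becomes 1 − (21/25)ρ = 1 − 0.84ρ. The test is then less conservative; simulated type I error is 2.4% and 1.2% at the same correlations. For any ρ > 0 the error rate lies below 5%.

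**5. Where pairing starts to pay, t-test.** The effect is held at 0.5 SD of a single swab (assumed). Power is unpaired v paired; the unpaired test uses every swab.

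| ρ | 30 complete pairs | 25 complete pairs | 21 pairs + 8 single swabs |
|---|---|---|---|
| 0 | 48 v 46% | 41 v 40% | 41 v 34% |
| 0.05 | 48 v 49% | 41 v 41% | not shown |
| 0.1 | 48 v 50% | 41 v 43% | 41 v 37% |
| 0.2 | not shown | not shown | 40 v 40% |
| 0.5 | not shown | not shown | 39 v 59% |

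With complete pairs the crossover is at about 0.05. It moves to about 0.2 at the maximal loss falling at random, because the paired t-test then discards 8 of the 50 swabs.

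**6. Keeping the single swabs.** A mixed model with a patient effect uses all 50. With variance components treated as known, its precision equals that of 21 + 4(1 − ρ) complete pairs: 25.0 at ρ = 0, 24.2 at 0.2 and 23.0 at 0.5. Most of the low-correlation drawback disappears.

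**7. PERMANOVA.** Simulations on several invented communities agree on direction. With substantial correlation, free permutation rejects too rarely under the null and has less power than within-patient permutation. They disagree widely on size. At correlation 0.5 (half the variance between patients), Bray-Curtis power was 20–49% v 67–85% in one set of communities (50 swabs v 21 pairs) and 3.6 v 37.2% in another (20 pairs). None of these figures should be read as a prediction for this study.

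**The case against.** The strongest reply is that this is an omission, not a wrong plan. The within-person comparison is the stated logic of the design, the list is drawn by patient, and 7.3 is too brief to exclude a paired analysis. The study calls itself exploratory and makes no power claim. All of that stands. It limits the point to what 7.3 leaves open, but it does not supply a test, a model term or a rule for a broken pair. The undertaking in 7.2 to look for biases due to randomisation does not do so either.

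The size is also open to challenge. The documents give no correlation. Below Figure 1, Section 1 concedes that "the environmental factors may differ between eyes", and left-right similarity is itself the third aim. At a correlation near zero the unpaired analysis does as well or slightly better, and more clearly so if single swabs are thrown away. This stands, and it is why only the direction is claimed.

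A reader might infer three stronger things that the documents do not support:
- That the plan prescribes an unpaired analysis. It does not; it is silent.
- That false positives are inflated. With positive correlation the error runs the other way.
- That Part 2 is compromised because its procedure relies on Part 1 results. Part 2 uses no anaesthetic drops, so a missed anaesthetic effect would not have put anaesthetic into its swabs.

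The 7.1 element is minor. Section 7.1 gives both 30 patients and 60 samples, no calculation uses the 50, and 20 to 25 pairs applies only at the maximal loss. The unstated handling of a single swab is the substantive gap there.

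**Conclusion.** The point holds as an omission with a known direction and an unknown size. Part 1 is randomised within patient, and 7.3 specifies nothing that uses this. If fellow eyes are positively correlated, as Section 1 expects, an analysis that ignores the pair is conservative and forgoes the gain from pairing. The consequence is confined to a null result on the first aim being harder to interpret.

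Confidence is high that the specification is missing, and low on how much power is at stake. The pair counts and detectable differences rest on the plan's numbers plus a two-sided 5% test at 80% power. The crossovers of about 0.05 and about 0.2 also assume a t-test, a 0.5 SD effect and, for the second, ten losses falling at random. This is a free improvement.

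**What to change.** In 7.3, for Part 1:
- Analyse Shannon and Simpson with a mixed model that has a patient random effect, which keeps single-swab patients, or as within-patient differences.
- Run PERMANOVA on complete pairs, with patient in the model and permutations restricted within patient. State that single-swab patients do not enter.

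In 7.1, add that 50 samples at the maximal loss means 20 to 25 complete pairs.

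The cost is a few sentences, or a re-run on existing data, with no further patients, swabs or assays. There is one limit. Version 7.0 is dated 01.02.2021, after the inclusion period planned in Section 3.3, and the Part 2 procedure in Section 2.1 reads as if Part 1 results were known. If Part 1 has already been analysed, label the paired analysis as specified after the data and report it beside the analysis already done.

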**Study Synopsis**

Title of clinical trial	Optimization of sampling for molecular microbial research on ocular surface samples and building a framework for comparing current sequencing results using different extraction protocols.
Protocol Short Title/Acronym	EPSO
Funding	LRD/ KU Leuven: EFW-FOPRD1-O2010 (Perdaens Eye Research Fonds) UZ Leuven: Fonds Academisch onderzoek S62672
Principal Investigator	[name]
Sponsor	University Hospitals Leuven [name]
Purpose of clinical trial	Optimization of ocular sampling for microbial research and to provide a framework for the interpretation of research results for ocular surface microbiome studies based on differences in DNA extraction procedures of complex microbial communities.
Trial Design	Exploratory study using biological samples
Summary of eligibility criteria	

• <math>\geq 18</math> years old

• Willing to undergo sampling of the conjunctiva

• Fluent in written and verbal Dutch

• Capable of giving informed consent

Study protocol EPSO v 7.0 dd 01.02.2021:

Optimization of sampling for molecular microbial research on ocular surface samples and building a framework for comparing current sequencing results using different extraction protocols.

Version and date of final protocol	v 7.0 dd 01.02.2021
------------------------------------	---------------------

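### Section 7.3 pre-specifies no taxon-level comparison, so Part 2 can show that extraction kits differ, and which gives higher diversity, but not which taxa each kit recovers relatively more or less of

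*Combined protocol and SAP*

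**What the plan says.** Section 7.3 (Analysis) is short and serves all three parts. On processing: "The sequences will be analysed using the latest bioinformatics tools (like Dada2) and analysis will be done with the R software". On outcomes: "The alpha diversity will be evaluated using Shannon's Diversity index and Simpson's diversity index", and "the beta diversity will be assessed by using Bray-Curtis dissimilarity, Jaccard distance and permutational multivariate analysis of variance". The significance threshold is 0.05. No taxonomic rank, differential-abundance or prevalence method, or kit-by-taxon estimate is named there or elsewhere in the protocol.

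Three places set out what Part 2 is for:

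- Section 2, objective 2, asks "how different DNA extraction protocols distort our view on ocular" surface microbiota composition.
- The Study Synopsis says the trial is meant to "provide a framework for the interpretation of research results for ocular surface microbiome studies based on differences in DNA extraction procedures".
- Section 1 motivates the kit comparison by noting that, in gut and oral research, the extraction method "plays a crucial role in the recovery of microbial taxa".

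Section 1 also describes the ideal extraction protocol in terms of richness and diversity. That is a whole-community criterion, which the alpha-diversity indices partly serve.

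**The concern.** Objective 2 asks how kits distort composition, which is more than whether they differ. Someone holding two published genus profiles, each obtained with a different kit, needs to know which genera tend to be higher or lower with one kit than with the other, and by roughly how much. Shannon and Simpson give one number per swab. Bray-Curtis and Jaccard give one unsigned number per pair of swabs, and PERMANOVA tests those distances as a whole. None names a taxon.

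If 7.3 is followed as written, the framework rests on statements such as kits differ in composition, or kit X gives lower diversity than kit Y. If taxa are examined anyway, the comparison is unplanned: seven protocols, many genera and an uncorrected 0.05 threshold leave wide room for selective reporting.

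**Working it through.** **Inputs from the protocol.** Part 2 has 7 volunteers × 7 days × 2 eyes = 98 swabs. There are six protocols, one of them with and without human depletion, so 7 are compared. Each volunteer-day uses one kit, giving 7 volunteers and 14 swabs per kit, and C(7,2) = 21 kit pairs. Section 7.1 gives no SD, effect size or power for Part 2, so there is no planned figure to reproduce.

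**What the listed measures return (invented profiles).** Kit A gives 60/25/10/5% and kit B 25/60/5/10% for the same four genera.

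- Shannon, −Σp ln p: 0.306 + 0.347 + 0.230 + 0.150 = 1.033 for both, because B contains the same four values in another order.
- Simpson, 1 − Σp²: 1 − (0.36 + 0.0625 + 0.01 + 0.0025) = 0.565 for both.
- Jaccard (presence/absence, assumed because 7.3 does not give the form): all four genera are present in both, so 0.
- Bray-Curtis, Σ|a − b| / Σ(a + b): (0.35 + 0.35 + 0.05 + 0.05)/2 = 0.40.

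Bray-Curtis sees the change but does not say which genus moved. The centred log-ratio does. The geometric means are equal, so the A-to-B fold differences are 60/25 = 2.4, 25/60 = 0.42, 10/5 = 2.0 and 5/10 = 0.5.

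**What the indices can do.** Shannon and Simpson carry a direction for diversity. An even community (25% each) gives 1.386 and 0.750, and a skewed one (70/10/10/10%) gives 0.940 and 0.480. They still name no taxon: 40/10/25/25% and 10/40/25/25% both give 1.290 and 0.705, and both lie at Bray-Curtis 0.15 from the even community although the distortions are opposite.

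**Is a taxon-level analysis feasible?**

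- *Model.* With eyes averaged there are 49 volunteer-visits. If each kit occurs once per volunteer and once per day, residual degrees of freedom are 48 − 6 − 6 − 6 = 30. The standard error of a kit difference is √(2/7) residual SD. The difference detectable with 80% power (two-sided noncentral t) is about 1.55 SD for one pair at 0.05, 2.25 SD with Bonferroni over 21 pairs, and 2.86 SD over 21 pairs × 20 genera (20 is an assumption).
- *Pairwise rank tests.* The smallest two-sided exact signed-rank p with 7 volunteers is 2/2⁷ = 0.0156. Multiplied by 21 it is 0.328, so such tests could never reach 0.05 after Bonferroni.
- *Multiplicity.* One uncorrected omnibus test per genus, treated as independent, gives a familywise error of 1 − 0.95^m: 0.40, 0.64 and 0.92 for 10, 20 and 50 genera.

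**Simulated range (all variances assumed).** The Part 2 layout was simulated with 30 genera, one of which is under-recovered four-fold by 2 of the 7 kits. Log-scale SDs were 1.0 between volunteers and 0.6 for visits and swabs unless stated. There were 150 trials per scenario, so the Monte Carlo error is at most about 4 points. Ranges are over different assumed abundance profiles and read-depth settings.

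| Scenario | PERMANOVA | Genus omnibus test with false discovery control |
|---|---|---|
| Genus at about 4% of reads | 7–13% | 83–89% |
| Genus at about 8% | 17–27% | 83–85% |
| About 8%, 1,000 reads per swab | 19% | 73% |
| Dominant genus | 67–72% | 79–81% |
| Visit and swab SDs 1.0 | not available | 23% |
| Visit and swab SDs 1.5 | not available | 7% |
| SDs 1.0, 300 reads per swab | 8% | 6% |
| Kits shift many genera (log SD 0.5) | 100% | not available |

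For the 4% genus with SDs of 0.6, contrasts of single kits against PowerSoil under false discovery control flagged both affected kits in 28% of trials and at least one in 47%.

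**The case against.** The strongest case for leaving 7.3 alone has five parts.

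1. *The indices serve a stated criterion.* Section 1 judges a kit by richness and diversity, and Shannon and Simpson show which kit gives more diversity. This stands. A reader might infer that 7.3 offers nothing with a direction, and that is not so. The gap is at taxon level.
2. *Without a known truth, no analysis can show over- or under-recovery.* This also stands. No mock community is described, and section 7.1 says the samples are too small to homogenise. A taxon-level analysis gives recovery relative to another kit, and the reference kit's own bias stays unknown.
3. *PERMANOVA is a reasonable overall test.* It is when kits shift many genera or a dominant one. A reader might infer that it will generally miss kit effects, or that the genus-level analysis is generally far more powerful. Neither is supported: the advantage depends on the assumed SDs, read depth and pattern of bias, and disappears in the noisiest settings.
4. *The study is exploratory, and the sequence output will allow taxonomic profiles to be described.* True, so it goes too far to infer that no framework could come out of these data. Being exploratory excuses the missing power calculation, but it does not supply an analysis for objective 2.
5. *A non-significant PERMANOVA need not be misread.* A reader might fear that it would be taken as agreement between kits, but no passage says it will be.

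Section 7.3 also cites two published studies, which could not be consulted. The plan does not say that their methods are adopted.

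**Conclusion.** The point holds as a gap in the pre-specified analysis. The listed measures can answer whether kits differ and which yields higher or lower diversity. They cannot answer which taxa a kit recovers relatively more or less of, although objective 2, the rationale and the framework all turn on composition. This follows from the definitions of the measures and needs no simulation; the four-genus profiles only illustrate it.

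How much a genus-level analysis would find cannot be settled from the documents, which give no variances or read depths. Over the assumptions examined, its omnibus test found the affected genus in between 6% and 89% of trials. Its value is therefore chiefly as estimates with intervals, not as a more powerful test. The data should already allow it, so the change is worth making, but its absence does not invalidate Part 2.

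**What to change.** Add one paragraph to section 7.3 for objective 2:

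- **Outcome:** centred log-ratio abundance (or another named compositional measure) of each genus that passes a preset prevalence filter, with a stated rule for zero counts and both eyes combined within volunteer-visit.
- **Model:** kit, volunteer and visit terms, with one omnibus kit test per genus and false discovery control over genera.
- **Main output:** a kit-by-genus table of fold differences relative to DNeasy PowerSoil, with 95% confidence intervals. PowerSoil is a natural reference because Part 1 uses it and section 2.1 says it was chosen for its frequency of use in the field.
- **Interpretation:** present the table as relative, not absolute, recovery, and state that power for single kit contrasts is limited with 7 volunteers.
- **Overall tests:** keep the diversity indices and PERMANOVA in that role.

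The genus rank, the transformation and the reference kit are choices the sponsor may vary, provided they are fixed before kit-labelled genus data are examined. If power is quoted, give it as a range over assumed SDs, read depths and patterns of bias.

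The cost is some extra analysis time and more tests. No further swabs or sequencing are needed.
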